## 5. Inclusion/Exclusion Criteria

### Inclusion criteria for FD patients

1. Bothersome postprandial fullness
2. Symptoms of early satiation, epigastric pain, epigastric burning during the last 3 months
3. No evidence of structural disease including at upper endoscopy that is likely to explain the symptoms.
4. Males and females between ages 18-80 yrs;
5. Subjects with high probability for compliance and completion of the study.

### Inclusion criteria for gastroparesis patients

1. At least one severe gastroparetic symptom or two moderate gastroparetic symptoms (see assessment of gastroparetic symptoms);
2. Abnormal gastric emptying diagnosed during the past year;
3. Males and females between ages 18-80 yrs;
4. Subjects with high probability for compliance and completion of the study.
5. Upper endoscopy or upper GI within last 2 years showing no evidence of gastric bezoar,

stricture, or peptic ulcer.

#### Inclusion criteria for chronic constipation patients

1. Satisfying Rome IV criteria for diagnosis of functional constipation;
2. abdominal X-ray or anorectal manometry test during the past 3 months indicating delayed colonic transit (more than 20% ingested markers are retained) or abnormal colonic motility;
3. ages 18-80 years;
4. no constipation medication for a minimum of 1 week before enrollment except for rescue agents (stimulant laxatives, such as bisacodyl);
5. willing to comply with the treatment regimen.

#### Exclusion criteria:

1. History of gastric bezoar or diverticulitis.
2. Severe daily abdominal pain requiring narcotic medications.
3. Previous gastro-esophageal surgery including vagotomy, fundoplication, gastric bypass, ulcer surgery.
4. Prior GI surgery except for uncomplicated appendectomy and laparoscopic cholecystectomy;
5. Surgery within the past 3 months.
6. pregnant or preparing to conceive a child;
7. Female of childbearing age who is not practicing birth control and/or is pregnant or lactating. (Confirm with urine pregnancy test).
8. Those who have been treated with acupuncture or those who are familiar with acupuncture points.
9. Anyone with an implantable cardiac pacemaker or defibrillator.
10. Allergic to skin preparation
11. unable to give informed consent;
12. taking prokinetics, anticholinergic or dopaminergic agents;
13. history of gastrointestinal surgery;

#### **6. Drugs/ Substances/ Devices**

- a. The rationale for choosing the drug and dose or for choosing the device to be used.

We have chosen previously validated questionnaires as our tools to monitor symptom response to TEA/Sham TEA. The tests used in the current protocol are also been validated and are part of the routine clinical care.

The microstimulator device used in the current protocol is a non-invasive device. It is developed under the support of previous NIH funding and has been used in the clinical study in an earlier project funded by NIH (Fig. 2)

- b. Justification and safety information if FDA approved drugs will be administered for non-FDA approved indications or if doses or routes of administration or participant populations are changed.

N/A

- c. Justification and safety information if non-FDA approved drugs without an IND will be administered.

N/A

## 7. Study Statistics

### a. Primary outcome variable.

The primary outcome of this study is GI symptoms including weekly GI symptom questionnaire; number of spontaneous complete bowel movement (SCBM) per week; and Patient Assessment of Constipation Symptoms (PAC-SYM), once every two weeks.

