### **Assessment of symptoms for patients with chronic constipation**

Symptoms: 1) Number of spontaneous complete bowel movement (SCBM) per week. 2) Patient Assessment of Constipation Symptoms (PAC-SYM). Stool diary during the entire experimental period to assess bowel movement, including number and time of defecation, stool quality, straining and medications or any other methods used for defecation; stool consistency will be assessed according to the Bristol Stool Form Scale. PAC-SYM questionnaire will be completed every two weeks. 3) Quality of life (PAC-QoL): the questionnaires will be completed at all visits.

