### c. Statistical plan including sample size justification and interim data analysis.

Analysis of the outcomes will use a repeated measures regression model including fixed effects for treatment, patient and time period. The model will be estimated using 8 weekly observations (weeks 1-4 and 7-10) on percentage changes in symptoms score from baseline visit (V0) levels for each subject. Results will be expressed as least squares means for the percentage change in symptoms score observe under each treatment, and statistical significance of any difference between these means will be determined with a model-based t-test. A weekly estimate of percentage compliance with the prescribed TEA-use regimen based on patient response to the TEA-use questionnaire will be included in the estimated model as a covariate to address possible confounding of treatment and compliance effects.

In the current protocol, 40 FD patients, 40 gastroparesis patients and 40 constipation patients will be enrolled. The accuracy of the planned patients sample in each disease was assessed by Monte Carlo stimulation. Each simulated sample assumed the percentage change in symptom score outcome is normally distributed with a standard deviation of 38 and a correlation of 0.4 across repeated observations on the same subject. This parameterization was based on previous data from a similar cross-over study by Liu et al. comparing the effects active and sham TEA administered with a conventional TENS device on changes in the same gastrointestinal symptom score in functional dyspeptic patients (14). Results of the power simulation indicate that with complete follow-up the planned sample provides an 80% chance of detecting a cross-treatment difference in symptom score change equal to 10-11 percentage points with a two-sided significance level of 0.05. Even if 40% of follow-up data are missing at random due to drop-outs or missed follow-up contacts, the simulation results indicate the planned experiment would still have an 80% chance of detecting a cross-treatment difference in symptom score change of 13-14 percentage points with a two-sided significance level of 0.05.

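### The constipation cohort has two unranked primary outcomes (SCBM and PAC-SYM) and no success rule; if either may support a claim, family-wise error is up to 9.75% rather than 5%.

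*Combined protocol and SAP*

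**What the plan says.** Section 7a (primary outcome variable) names the weekly GI symptom questionnaire and then adds "number of spontaneous complete bowel movement (SCBM) per week; and Patient Assessment of Constipation Symptoms (PAC-SYM), once every two weeks". It does not rank the measures or assign them to diseases. The assignment comes from section 4, under the heading on symptom assessment in chronic constipation, where SCBM per week and PAC-SYM are the first two items. The same paragraph says "PAC-SYM questionnaire will be completed every two weeks". Section 7b does not move either one to the secondary list.

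Section 7c describes the analysis for every outcome together: "Analysis of the outcomes will use a repeated measures regression model including fixed effects for treatment, patient and time period". The data are described once: "The model will be estimated using 8 weekly observations (weeks 1-4 and 7-10) on percentage changes in symptoms score". The decision step is "statistical significance of any difference between these means will be determined with a model-based t-test", with no level attached. The level appears only in the two power sentences, for example "symptom score change equal to 10-11 percentage points with a two-sided significance level of 0.05".

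The plan gives no order of testing, no requirement that both measures succeed, no combined score, no split of alpha and no multiplicity method.

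**The concern.** The same 40 constipation patients supply two primary results on one question: does TEA help constipation? With no success rule, whoever reports the trial may present a significant SCBM result, a significant PAC-SYM result, or both, as meeting the primary outcome. If one of the two is enough and each is tested at 0.05, the constipation claim no longer carries a 5% error rate. The choice of which outcome to emphasise can also be made after the results are seen.

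The problem lies within the constipation cohort. The three diseases have separate patients, and section 7c assesses the sample size for each disease, so they can reasonably be read as separate questions.

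**Working it through.** **Inputs from the documents.** 40 patients per disease in a two-period crossover; 8 weekly observations, 4 per period; SD 38 percentage points; correlation 0.4 across repeated observations; two-sided 0.05; 80% power (all section 7c, with the crossover in section 4a). PAC-SYM is collected every two weeks (sections 4 and 7a).

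**Assumption.** The documents give no correlation r between the SCBM and PAC-SYM test statistics, so a range of 0 to 0.9 is used. Only its absolute size matters for two-sided tests, so it is no obstacle that improvement means a higher SCBM and a lower PAC-SYM score.

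**1. The plan's own figure.** The plan states no family-wise error rate. Its one checkable figure is the detectable difference of 10-11 points with complete follow-up. With equal correlation among all of a patient's observations:

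SE = sqrt(38² × (1 − 0.4) × (1/4 + 1/4) / 40) = sqrt(10.83) = 3.29

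Detectable difference = 3.29 × (1.960 + 0.842) = 3.29 × 2.802 = 9.2 points

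This is slightly better than the stated 10-11, at which the same formula gives power of 0.86 to 0.92. With 40% of data missing, simulating the fixed-effects model reaches 80% power near 13 points (scattered missing observations) or 13.5-14 (dropout), in line with the stated 13-14. The plan does not describe its simulation's covariance structure or how the compliance covariate was handled, so the gap is not called an error. It does not affect what follows.

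**2. Family-wise error if either outcome suffices.** Both nulls true, each test two-sided at 0.05, bivariate normal statistics:

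FWER = 1 − P(|Z1| < 1.96 and |Z2| < 1.96)

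At r = 0 this is 1 − 0.95² = 0.0975.

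| Assumed r | FWER | Multiple of 5% |
|---|---|---|
| 0 | 9.75% | 1.95 |
| 0.3 | 9.5% | 1.9 |
| 0.5 | 9.1% | 1.8 |
| 0.7 | 8.3% | 1.7 |
| 0.8 | 7.8% | 1.6 |
| 0.9 | 7.0% | 1.4 |

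These figures count a false result in either direction. Counting only results that favour TEA, the single-test rate is 2.5% and the rate for two tests is 4.94% at r = 0 and 3.5% at r = 0.9, so the relative inflation is much the same.

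**3. Cost of Holm.** The smaller p-value is compared with 0.025 and, if it passes, the other with 0.05. At worst, an outcome needs the 0.025 threshold:

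(2.241 + 0.842) / (1.960 + 0.842) = 3.083 / 2.802 = 1.10

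The stated 10-11 points become about 11.0-12.1. At the difference that had 80% power, power at the 0.025 threshold is Φ(2.802 − 2.241) = Φ(0.561), or about 71%. Error with both tests at 0.025 is 1 − 0.975² = 4.94% at r = 0.

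**4. PAC-SYM against the model.** Collection every two weeks gives about 2 observations per 4-week period, or 4 in all, against the model's 8. With the same SD and correlation:

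SE = sqrt(38² × 0.6 × (1/2 + 1/2) / 40) = sqrt(21.66) = 4.65; detectable difference = 4.65 × 2.802 = 13.0 points, against 9.2

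This is only indicative, because the SD and correlation come from a symptom score in functional dyspepsia, not from PAC-SYM.

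**The case against.** The strongest reply is that the plan never says either result alone would suffice. Section 7a speaks of a primary outcome in the singular, GI symptoms, measured in several ways. Silence is also compatible with requiring both measures to succeed. Under that rule the error is at most 5%, and with both nulls true it is only 0.25% at r = 0 and 3.0% at r = 0.9. This part stands: the inflation depends on the either-suffices reading. But the plan does not state the stricter rule either, and it gives no way to combine a weekly count and a two-weekly questionnaire into one outcome.

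A reader might infer several stronger things that the documents do not support:

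- *That section 7c tests each outcome at 0.05.* It does not say so. The level appears only in the power sentences, which concern a symptom score; the analysis sentence carries no level. Using 0.05 per outcome is a reasonable inference, since no other level is given.
- *That the error rate nearly doubles.* That is the independence case and the upper end of the range. Both outcomes measure the same condition in the same patients, so some correlation is likely.
- *That there are three primaries in this cohort.* Section 4a can be read as giving the gastroparesis symptom questionnaire to everyone, and three independent tests would give 1 − 0.95³ = 14.3%. But the same section says constipation-related symptoms are assessed in these patients, and Table 1 is limited to FD and gastroparesis. The point does not rely on this reading.
- *That error should be pooled over all three diseases.* Each disease has its own patients and its own sample-size assessment, so a pooled rate is not the relevant quantity.

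**Conclusion.** The concern holds as an unstated success rule for two primary outcomes in one cohort. Followed as written, the plan does not secure 5% error control for a constipation claim. The family-wise error is up to 9.75%, and about 7.0% to 9.75% for r from 0.9 to 0. This rests on two inferences (either result suffices, and each is tested at two-sided 0.05) and on an assumed correlation. Error exceeds 5% over the whole range considered. The design is not invalidated, and the gap can be closed before analysis, so this is a change the plan should make rather than a fatal fault.

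**What to change.** Amend sections 7a and 7c before any analysis. Both sit in the protocol form, so this is a protocol amendment.

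1. In section 7a, assign each primary measure to its disease.
2. For constipation, control error at two-sided 0.05 across SCBM and PAC-SYM by one stated rule: test them in a fixed order, each at 0.05, going to the second only if the first is significant; or name one primary and make the other secondary; or apply Holm across the two.
3. State that FD, gastroparesis and constipation are separate questions, each at two-sided 0.05.
4. Define the PAC-SYM test on its two-weekly observations, and say how the weekly SCBM count enters a model written for percentage change in a symptom score. No multiplicity rule can be applied cleanly until both tests are defined.

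**Cost.** No extra patients or visits are needed for the rule itself. A fixed order costs the first outcome no power, but the second cannot be claimed if the first fails. Making one measure secondary means giving up a primary claim on it. Holm keeps both open and raises the detectable difference by at most about 10%. Item 4 may show that PAC-SYM has less power than the stated figures suggest.

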### b. Secondary outcome variables.

The secondary outcome measure of the study will include:

1. TEA use questionnaire.

2. Monthly assessment of quality of life questionnaire.

3. Autonomic functions,

4. GI hormones.

### c. Statistical plan including sample size justification and interim data analysis.

Analysis of the outcomes will use a repeated measures regression model including fixed effects for treatment, patient and time period. The model will be estimated using 8 weekly observations (weeks 1-4 and 7-10) on percentage changes in symptoms score from baseline visit (V0) levels for each subject. Results will be expressed as least squares means for the percentage change in symptoms score observe under each treatment, and statistical significance of any difference between these means will be determined with a model-based t-test. A weekly estimate of percentage compliance with the prescribed TEA-use regimen based on patient response to the TEA-use questionnaire will be included in the estimated model as a covariate to address possible confounding of treatment and compliance effects.

In the current protocol, 40 FD patients, 40 gastroparesis patients and 40 constipation patients will be enrolled. The accuracy of the planned patients sample in each disease was assessed by Monte Carlo stimulation. Each simulated sample assumed the percentage change in symptom score outcome is normally distributed with a standard deviation of 38 and a correlation of 0.4 across repeated observations on the same subject. This parameterization was based on previous data from a similar cross-over study by Liu et al. comparing the effects active and sham TEA administered with a conventional TENS device on changes in the same gastrointestinal symptom score in functional dyspeptic patients (14). Results of the power simulation indicate that with complete follow-up the planned sample provides an 80% chance of detecting a cross-treatment difference in symptom score change equal to 10-11 percentage points with a two-sided significance level of 0.05. Even if 40% of follow-up data are missing at random due to drop-outs or missed follow-up contacts, the simulation results indicate the planned experiment would still have an 80% chance of detecting a cross-treatment difference in symptom score change of 13-14 percentage points with a two-sided significance level of 0.05.

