Upon enrollment, each patient will be randomly assigned to group A or group B. Patients in group A will be treated with TEA at ST36 and PC6 for 4 weeks, followed with a 2-week washout period and another 4-week period with sham TEA. Patients in group B will be treated with TEA and sham-TEA in a reversed order. The previous preliminary studies with EA or TEA were of duration of 2 weeks. To ensure better performance, we choose a treatment period of 4 weeks. A previous study has indicated that a washout period of 2 weeks is sufficient. The patients will not be informed of the exact locations of ST36 or PC6 and will not be informed that TEA at the sham points may be ineffective. The patients will be asked to come to the hospital 4 times: before the study (V1), end of the first 4 weeks (V2), end of washout period or beginning of the second 4-weeks (V3) and end of the second 4 weeks (V4). TEA or sham TEA will be performed three times daily, each initiated immediately after a meal and lasts for 2 hours. Various tests will be performed during each visit (see Fig.1 and Table 1). Symptoms of gastroparesis, assessment of constipation and questionnaire of quality of life (SF-36) as well as

TEA usage questionnaire will be completed during each of the 4 visits. The questionnaires will also be completed by the patient at home at the end of each week including the washout period.

The procedure for each visit is as follows: In the morning, GI symptom questionnaire, TEA use and SF-36 will be completed; then chest and abdominal surface electrodes will be placed and the noninvasive measurements of electrogastrogram (EGG) will be recorded for 2 hours. One hour after the recording, a test meal will be consumed by the subject and the recording will be continued for one more hour. Blood samples will be taken to measure gastrointestinal hormones such as NPY, ghrelin, CCK, motilin and VIP at different time points: at the initiation of the baseline recording of the EGG, immediately before the ingestion of the meal, 30 and 60min after the test meal. TEA or sham-TEA (according to the preceding treatment regime) will be performed during the tests for visits 2 and 4. No TEA or sham-TEA will be performed during visits 1 and 3 as these tests will be considered as baseline or control tests. For the patients with chronic constipation, no nutrient drink test will be conducted, symptoms related to constipation will be assessed, EGG will be recorded and blood samples will be collected.

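### In the constipation group, spontaneous complete bowel movements (SCBMs) per week is a primary outcome whose only available analysis, percentage change from baseline, has no value at a baseline of zero; read otherwise, it has no stated analysis

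*Combined protocol and SAP*

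**What the plan says.** Section 7a (Primary outcome variable) names GI symptoms as primary. It lists a weekly GI symptom questionnaire and then "number of spontaneous complete bowel movement (SCBM) per week; and Patient Assessment of Constipation Symptoms (PAC-SYM), once every two weeks". Section 4a (Assessment of symptoms for patients with chronic constipation) puts the SCBM count first under symptoms, separate from PAC-SYM, and has a stool diary running through the whole study.

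Section 7c holds the only analysis text. It applies a repeated-measures regression to the outcomes, with treatment, patient and period as fixed effects and a weekly compliance estimate as a covariate. The model uses eight weekly values per patient (weeks 1-4 and 7-10), and the response is "percentage changes in symptoms score from baseline visit (V0) levels for each subject". Results are least squares means of that percentage change, compared by a t-test.

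The power statement in 7c assumes an SD of 38 and a within-patient correlation of 0.4, taken from a crossover study of "the same gastrointestinal symptom score in functional dyspeptic patients". It gives detectable differences of 10-11 points with complete data and 13-14 points with 40% missing.

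Section 5 lists five entry criteria for constipation: "Satisfying Rome IV criteria for diagnosis of functional constipation", a transit or motility finding, an age range, a limit on prior constipation medication, and willingness to comply. None states a minimum SCBM count.

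**The concern.** A percentage change divides by the baseline value. SCBMs per week is a count with a floor at zero, and the trial recruits patients because they are constipated, so a baseline of zero is an ordinary possibility. The plan gives no rule for it.

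If undefined values are simply omitted, the analysis set is selected on baseline severity. If a constant is added or the scale is changed, the primary result depends on a choice the plan does not record. Section 4c says the investigators cannot practically be blinded, and section 7d has the principal investigator reviewing data as they arrive, so an unwritten rule would be hard to defend.

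**Working it through.** **1. The plan's own power figure.** Inputs from section 7c: n = 40 per disease, SD 38, correlation 0.4, four weekly values per treatment, two-sided 0.05, 80% power.

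- Complete data: SE = sqrt(2 × 38² × (1 − 0.4) / (40 × 4)) = sqrt(1732.8 / 160) = 3.29. Detectable difference = (1.960 + 0.842) × 3.29 = 9.2 points, against the stated 10-11.
- 40% missing: SE = sqrt(10.83 / 0.6) = 4.25, giving 11.9 points, against 13-14. A simulation with patient and week effects gives about 82% power at 13 points and 87% at 14 with scattered missing values, and about 74% and 79% with dropout. The stated range is therefore roughly matched.

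The complete-data figure is not reproduced exactly, but it errs on the cautious side and is a separate matter. What counts here is that all of these figures are percentage points of a dyspepsia symptom score. None describes SCBM.

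**2. The response at zero.** With baseline b and weekly value x, the response is 100 × (x − b) / b. It has no value at b = 0, whatever x is.

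**3. Can b be zero?** Nothing in the five criteria as written prevents it. The baseline counting window is not stated either. Section 4a places a constipation assessment at V1 and a diary throughout, but Table 1 covers only FD and gastroparesis, and Fig. 1 was not available here.

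**4. How many patients?** The documents give no SCBM rate, so this is an assumed range. With mean m per week and a window of w weeks, a Poisson count gives P0 = exp(−m·w). Adding a between-patient CV of 0.7 (gamma-Poisson, k = 1/0.49) gives P0 = (k / (k + m·w))^k. Expected zero-baseline patients = 40 × P0:

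| Mean per week | Poisson, 1 week | Poisson, 2 weeks | CV 0.7, 1 week | CV 0.7, 2 weeks |
|---|---|---|---|---|
| 0.5 | 24.3 | 14.7 | 25.6 | 17.7 |
| 1 | 14.7 | 5.4 | 17.7 | 9.9 |
| 2 | 5.4 | 0.7 | 9.9 | 4.4 |
| 3 | 2.0 | 0.1 | 6.3 | 2.4 |

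A zero share of only 5% gives a chance of 1 − 0.95^40 = 87% that at least one of 40 patients is undefined.

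**5. Who is dropped?** With CV 0.7 and a one-week window, for means 0.5 / 1 / 2 / 3, the dropped patients have mean true rates of 0.40 / 0.67 / 1.01 / 1.21 per week. Those kept have 0.67 / 1.26 / 2.33 / 3.33. If all patients shared one true rate, the loss would be by chance. Once patients differ, it falls on those with the fewest movements.

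**6. The other reading.** If the symptom score excludes SCBM, steps 2 to 5 do not apply. But 7c then contains no response, model or effect measure for SCBM.

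**7. Is the division needed?** No. On the count scale, subtracting b from every value of a patient is absorbed by that patient's fixed effect, so the TEA-sham contrast is the same with or without the baseline.

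**The case against.** The best defence is that 7c opens by applying its model to the outcomes generally, that its treatment, patient and period structure suits SCBM, and that any competent analyst would settle the zeros. SCBM is also one of three listed primary measures, for one of three disease groups, and the number of zeros could be close to none. The limit on scope and the uncertainty about size both stand. The defence does not remove the gap: the general opening leads straight to the percentage response, which is where zero fails.

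Several stronger inferences are tempting and are not supported:

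- **That the whole trial is affected.** The zero-count argument does not reach the FD and gastroparesis symptom-score analyses.
- **That the percentage scale costs a known amount of power.** The answer changes with whether benefit is the same number of SCBMs for every patient or proportional to each patient's rate. The documents say nothing on this, so no efficiency figure is offered.
- **That the zero rule will be chosen after seeing data.** The documents show only that no rule is pre-specified; one could still be fixed beforehand.
- **That PAC-SYM is plainly also scheduled weekly.** Section 4a does say "The questionnaires will also be completed by the patient at home at the end of each week including the washout period", but this cannot be literal for every instrument: SF-36 is in the same list, yet Table 1 shows it only at visits.
- **That V0 is a missing visit.** Table 1 labels week 0 as V1, so V0 is probably a slip.

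**Conclusion.** The point holds for SCBM in the constipation group. The natural reading, supported by sections 4a and 7a placing SCBM among the symptoms, yields a primary response that is undefined for patients the entry criteria allow, with no rule for them. The alternative reading leaves a primary outcome without an analysis. This conclusion rests on the text alone.

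The size does not. The span of about 0.1 to 26 of 40 depends entirely on the assumed mean rate, baseline window and between-patient spread. At the favourable end (Poisson, mean 3, two weeks) there would most likely be no affected patient, and the consequence would be nil in practice although the rule would still be missing. Confidence is high that the gap exists and low about how much it would change the result.

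A side note of the same kind: section 4a says "PAC-SYM questionnaire will be completed every two weeks", which gives about two values per four-week treatment period, four in all. PAC-SYM therefore cannot supply the eight weekly values that the model uses.

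**What to change.** Amend section 7c before SCBM data are examined:

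1. Analyse SCBMs per week in weeks 1-4 and 7-10 on the count scale, with the plan's treatment, period and patient effects, and report the TEA-sham difference in SCBMs per week. No patient is then excluded because of a zero baseline, although the within-patient contrast still needs diary data under both treatments. A count model with random patient effects is an alternative; name one as primary.
2. State whether the weekly compliance covariate is kept in this model.
3. State that the SD of 38 and the detectable differences of 10-11 and 13-14 points come from a dyspepsia symptom score and do not cover SCBM or PAC-SYM.
4. Fit the PAC-SYM model to the times at which it is actually collected.
5. Replace V0 with V1, if that is the visit meant.

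The cost is plan wording only, with no added visits or data. The downside is that SCBM results will not be in percent and SCBM will have no stated power unless separate planning data are found. If none are, label the outcome as outside the power calculation.
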